6.2 Exclusion Criteria

- 1) Target Disease Exclusions
 - a) Participants with primary CNS disease, or tumors with CNS metastases as the only site of disease, will be excluded. Participants with controlled brain metastases, however, will be allowed to enroll. Controlled brain metastases are defined as no radiographic progression for at least 4 weeks following radiation and/or surgical treatment (or 4 weeks of observation if no intervention is clinically indicated), and no longer taking steroids for at least 2 weeks prior to first dose of study drug, and with no new or progressive neurological signs and symptoms.
 - b) Participants in Part 2C with known EGFR mutations which are sensitive to available targeted inhibitor therapy (including, but not limited to, deletions in exon 19 and exon 21 [L858R] substitution mutations) are excluded. All participants with non-squamous histology must have been tested for EGFR mutation status; use of an FDA-approved test

is strongly encouraged. Participants with non-squamous histology and unknown or indeterminate EGFR status are excluded.

c) Participants in Part 2C with known ALK translocations which are sensitive to available targeted inhibitor therapy are excluded. If tested, use of an FDA-approved test is strongly encouraged.

2) Prohibited Treatments

- a) Cytotoxic agents, unless at least 4 weeks have elapsed from last dose of prior anti-cancer therapy and initiation of study therapy
- b) Noncytotoxic agents, unless at least 4 weeks or 5 half-lives (whichever is shorter) have elapsed from the last dose of prior anti-cancer therapy and the initiation of study therapy. If 5 half-lives is shorter than 4 weeks, agreement with Sponsor/Medical Monitor is mandatory
- c) Prior immune therapy treatments, unless at least 4 weeks or 5 half-lives (whichever is shorter) have elapsed from the last dose of immune therapy and initiation of study therapy
- d) Prior participation in an anti-TIGIT clinical study

3) Prior anti-cancer treatments such as chemotherapy, radiotherapy, hormonal, or immunotherapy (including anti-PD1/PD-L1) are permitted (except for NSCLC participants in Part 2C).

4) Medical History and Concurrent Diseases

- a) Participants with concomitant second malignancies (except adequately treated nonmelanomatous skin cancers or in situ bladder, breast, or cervical cancers) are excluded unless a complete remission was achieved at least 2 years prior to study entry, and no additional therapy is required or anticipated to be required during the study period
- b) Participants with other active malignancy requiring concurrent intervention
- c) Prior organ allograft
- d) Toxicity (except for alopecia) related to prior anti-cancer therapy and/or surgery, unless the toxicity is either resolved, returned to baseline or Grade 1, or deemed irreversible
 - i) Any active neuropathy > Grade 2 (NCI CTCAE v4.03)
- e) Participants with the following:
 - i) Active, known, or suspected autoimmune disease
 - Participants with well controlled asthma and/or mild allergic rhinitis (seasonal allergies) are eligible
 - Participants with the following disease conditions are also eligible:
 - Vitiligo
 - Type 1 diabetes mellitus
 - Residual hypothyroidism due to autoimmune condition only requiring hormone replacement
 - Euthyroid participants with a history of Grave's disease (participants with suspected autoimmune thyroid disorders must be negative for thyroglobulin)

and thyroid peroxidase antibodies and thyroid stimulating Ig prior to the first dose of study drug)

- Psoriasis not requiring systemic treatment, or conditions not expected to recur in the absence of an external trigger are permitted to enroll.
- ii) History of life-threatening toxicity related to prior immune therapy (eg, anti-CTLA-4 or anti-PD-1/PD-L1 treatment or any other antibody or drug specifically targeting T cell co-stimulation or immune checkpoint pathways) except those that are unlikely to re-occur with standard countermeasures (eg, hormone replacement after adrenal crisis).
- iii) Conditions requiring systemic treatment with either corticosteroids > 10 mg daily prednisone equivalents or other immunosuppressive medications within 14 days of study drug administration, except for adrenal replacement steroid doses ≤ 10 mg daily prednisone equivalent in the absence of active autoimmune disease.
 - Treatment with a short course of steroids (< 5 days) up to 7 days prior to initiating study drug is permitted
- iv) Uncontrolled or significant cardiovascular disease including, but not limited, to any of the following:
 - Myocardial infarction or stroke/transient ischemic attack within the past 6 months
 - Uncontrolled angina within the past 3 months
 - Any history of clinically significant arrhythmias (such as ventricular tachycardia, ventricular fibrillation, or torsades de pointes)
 - History of other clinically significant heart disease (eg, cardiomyopathy, congestive heart failure with New York Heart Association functional classification III to IV [[Appendix 9](#)] pericarditis or significant pericardial effusion)
 - Cardiovascular disease-related requirement for daily supplemental oxygen therapy
 - QT interval corrected for heart rate using Fridericia's formula (QTcF) prolongation > 480 msec, except for right bundle branch block
 - History of myocarditis, regardless of etiology
- v) History of chronic hepatitis (except for HCC) as evidenced by the following:
 - Positive test for hepatitis B surface antigen
 - Positive test for qualitative hepatitis C viral load by PCR
 - Participants with positive hepatitis C antibody and negative quantitative hepatitis C by PCR are eligible. History of resolved hepatitis A virus infection is not an exclusion criterion.
 - Additional testing or substitute testing per institutional guidelines to rule out infection is permitted.
 - **Specific exclusions for participants with HCC:**
 - Active coinfection with both hepatitis B and C

- Hepatitis D infection in participants with hepatitis B
- Clinically significant ascites or clinically significant variceal bleeding

vi) Evidence of active infection that requires systemic antibacterial, antiviral, or antifungal therapy \leq 7 days prior to the first dose of study drug (except for viral infections that are presumed to be associated with the underlying tumor type required for study entry)

vii) Known history of testing positive for HIV or known acquired immunodeficiency syndrome
Note: Testing for HIV must be performed at sites where mandated by local requirements.

viii) Any major surgery within 4 weeks of the first dose of study drug. Participants must have recovered from the effects of major surgery or significant traumatic injury at least 14 days before the first dose of study drug.

ix) Receipt of nononcology vaccines containing live virus for prevention of infectious diseases within 4 weeks prior to first dose of study drug

- (1) The use of inactivated seasonal influenza vaccines, eg, Fluzone®, will be permitted on study without restriction.
- (2) Previous SARS-CoV-2 vaccine within 14 days of C1D1 is not permitted.

x) Receipt of packed red blood cells or platelet transfusion within 2 weeks of the first dose of study drug unless agreed by the medical monitor.

xi) Any known or underlying medical, psychiatric condition and/or social reason that, in the opinion of the Investigator or Sponsor, could make the administration of study drug hazardous to the participants or could adversely affect the ability of the participant to comply with or tolerate the study.

xii) Participant has any condition, including active or uncontrolled infection, or the presence of laboratory abnormalities, which places the participant at unacceptable risk if he/she were to participate in the study

xiii) Previous SARS-CoV-2 infection within 10 days for mild or asymptomatic infections or 20 days for severe/critical illness prior to C1D1.

- (3) Acute symptoms must have resolved and based on investigator assessment in consultation with the medical monitor, there are no sequelae that would place the participant at a higher risk of receiving study treatment.

f) WOCBP who are pregnant or breastfeeding

5) Allergies and Adverse Drug Reaction

- a) History of allergy to study drug components
- b) History of severe hypersensitivity reaction to any mAb

6) Other Exclusion Criteria

- a) Prisoners or participants who are involuntarily incarcerated. (Note: under certain specific circumstances a person who has been imprisoned may be included or permitted to continue as a participant. Strict conditions apply and Sponsor approval is required.)
- b) Participants who are compulsorily detained for treatment of either a psychiatric or physical (eg, infectious disease) illness

Eligibility criteria for this study have been carefully considered to ensure the safety of the study participants and that the results of the study can be used. It is imperative that participants fully meet all eligibility criteria.

6.3 Lifestyle Restrictions

There are no lifestyle restrictions applicable for this study given that the participants will receive the study investigational products (IPs) IV.

6.4 Screen Failures

Screen failures are defined as participants who consent to participate in the clinical study but are not subsequently randomized/entered in the study. A minimal set of screen failure information is required to ensure transparent reporting of screen failure participants, to meet the Consolidated Standards of Reporting Trials (CONSORT) publishing requirements ([Appendix 10](#)), and to respond to queries from regulatory authorities. Minimal information includes date of consent, demography, screen failure details, eligibility criteria, and any SAEs.

6.4.1 Retesting During Screening or Lead-In Period

This study allows for the re-enrollment of a participant that has discontinued the study as a pretreatment failure. Retesting of laboratory parameters and/or other assessments during the extended screening period will be allowed.

The most current result prior to enrollment is the value by which study inclusion will be assessed, as it represents the participant's most current, clinical state.

Testing for asymptomatic SARS-CoV-2 infection by RT-PCR or viral antigen is not required. However, some participants may develop suspected or confirmed symptomatic SARS-CoV-2 infection, or be discovered to have asymptomatic SARS-CoV-2 infection during the screening period. In such cases, participants may be considered eligible for the study after meeting all inclusion/exclusion criteria related to active infection, and after meeting the following criteria:

- At least 10 days (20 days for severe/critical illness) have passed since symptoms first appeared or positive RT-PCR or viral antigen test result, and
- At least 24 hours have passed since last fever without the use of fever-reducing medications, and
- Acute symptoms (e.g. cough, shortness of breath) have resolved and
- In the opinion of the investigator, there are no SARS-CoV-2 infection sequelae that may place the participant at a higher risk of receiving investigational treatment

In the instance of a SARS-CoV-2 infection during screening, the screening period may be extended beyond the protocol-specified timeframe with Medical Monitor approval. Any screening tests already performed which could potentially be affected by the SARS-CoV-2 infection or its complications on an individual basis and agreed upon with the Medical Monitor (eg, safety labs, oxygen saturation, chest CT scan) should be repeated.

7. TREATMENT

7.1 Treatments Administered

Study treatment is defined as any investigational treatment(s), marketed product(s), placebo or medical device intended to be administered to a study participant according to the study randomization or treatment allocation.

An IP, also known as investigational medicinal product in some regions, is defined as a pharmaceutical form of an active substance or placebo being tested or used as a reference in a clinical study, including products already with a marketing authorization but used or assembled (formulated or packaged) differently than the authorized form, or used for an unauthorized indication, or when used to gain further information about the authorized form.

Other medications used as support or escape medication for preventative, diagnostic, or therapeutic reasons, as components of the standard of care for a given diagnosis, may be considered as noninvestigational products.

All drugs used in this open-label study qualify as IPs, as per previous text, and their description and storage information are described in Table 7.1-1.

Table 7.1-1: Study Drugs

Product Description Class and Dose Form	Potency	Blinding	Packaging Appearance	Storage Conditions (per Label)
BMS-986207 for injection ^a	160 mg/vial (20 mg/mL)	None	Vial	2 to 8°C. Protect from light and freezing.
Nivolumab (BMS-936558) solution for injection ^a	100 mg/vial (10 mg/mL)	None	Vial	2 to 8°C. Protect from light and freezing.
Ipilimumab (BMS-734016) solution for injection ^a	200 mg (5 mg/mL)	None	Vial	2 to 8°C. Protect from light and freezing.

Abbreviation: BMS = Bristol-Myers Squibb; C = Celsius; IP = investigational product

^a All study drugs are considered IPs

For Parts 1A, 1B, 2A and 2B, the initial treatment period is up to 24 weeks (3 cycles) of dosing. Following each treatment cycle, the decision to treat a participant with the next cycle of study therapy, up to a maximum of 48 weeks (6 cycles) of treatment, will be based on risk/benefit

analysis and tumor assessment. For Parts 1C and 2C, the treatment period is up to a maximum of 2 years in the absence of disease progression or unacceptable toxicity.

Upon completion of treatment, participants will enter a safety follow-up period. Details of the dose escalation and cohort expansion phases in this study are given as part of the study design in [Section 5](#). The selection and timing of dose for each participant are as shown in Table 7.1-2.

Table 7.1-2: Selection and Timing of Dose

Study Treatment	Participant Weight	Dosage formulation Frequency of Administration	Route of Administration	Infusion Time (min)
BMS-986207^a				
80 mg	Any	Infusion q2w	IV	60
200 mg	Any	Infusion q3w	IV	60
240 mg	Any	Infusion q2w	IV	60
360 mg	Any	Infusion q3w	IV	60
480 mg	Any	Infusion q4w	IV	60
600 mg	Any	Infusion q3w	IV	60
600 mg	Any	Infusion q4w	IV	60
800 mg	Any	Infusion q2w	IV	60
1200 mg	< 38 kg	Infusion q3w	IV	90
1200 mg	≥ 38 kg	Infusion q3w	IV	60
1600 mg	< 42 kg	Infusion q2w and q4w	IV	90
1600 mg	≥ 42 kg	Infusion q2w and q4w	IV	60
Nivolumab				
240 mg	Any	Infusion q2w	IV	30
360 mg	Any	Infusion q3w	IV	30
480 mg	Any	Infusion q4w	IV	30
Ipilimumab				
1 mg/kg	Any	Infusion q6w	IV	30

Abbreviations: IV, intravenous; q2w, every 2 weeks; q3w, every 3 weeks; q4w, every 4 weeks; q6w, every 6 weeks.

^a If dose-de-escalation is recommended by the design based on the number of participants with DLTs observed during this dose evaluation phase ([Table 5.1.2.6-1](#)), then the next lower dose level will be used (360 mg BMS-986207 q3w) for the remaining participants. In addition, other lower doses of BMS-986207 (200 mg q3w) than that seen as safe and tolerable may also be tested.

For participants < 42 kg on the 1600 mg dose, the infusion time will be 90 minutes. Details of study drug preparation are found in the Pharmacy Manual, a document that will be provided separately to the site.

For participants on combination treatment, a 30-minute infusion of nivolumab will be followed by a 30-minute observation period, followed by a 60-minute infusion of BMS-986207 and a 60-minute observation period after all infusions in Cycle 1 for each participant. A 60-minute post-infusion safety observation period is considered appropriate given BMS-986207 is fully human.

antibody that is an antagonist antibody (not an agonist antibody) and has a low likelihood of resulting in infusion reactions. For participants in the Triplet Cohort (Part 1C) and Triplet NSCLC Expansion (Part 2C), a 30-minute infusion of nivolumab will be followed by a 30-minute observation period, followed by a 30-minute infusion of ipilimumab, a 30-minute observation period, followed by a 60-minute infusion of BMS-986207.

For participants < 38 kg on the 1200 mg dose, the infusion time will be 90 minutes. For participants with a bodyweight of > 250 kg the dosing of BMS-986207 will occur the day after dosing of nivolumab and ipilimumab when these drugs are administered on the same day. Details of study drug preparation are found in the Pharmacy Manual.

7.2 Method of Treatment Assignment

In this open-label study, enrolled participants, including those not dosed, will be assigned via IRT sequential participant numbers starting with [REDACTED] (eg, [REDACTED]). Those enrolled participants meeting the inclusion criteria, and none of the exclusion criteria, will be eligible to be dosed. Sequential numbering may restart at [REDACTED] for each participating site as the distinct participant identification number will ultimately comprise of the site number and participant number, (eg, [REDACTED]). In the expansion phase only, participants with CRC will be randomized in a 1:1 manner to either BMS-986207 monotherapy, or combination therapy with BMS-986207 and nivolumab, to eliminate the possibility of enrollment bias.

Participants in Part 2C with 1L NSCLC and tumor cell PD-L1 expression of $\geq 1\%$ based on pre-existing lab results will be enrolled to receive combination therapy with BMS-986207, nivolumab, and ipilimumab. If more than 25% of the participants have a PD-L1 score < 1% as determined by the central lab, additional participants may be enrolled in order to have at least 30 participants with a tumor cell score of $\geq 1\%$.

Participants will not be replaced if they are discontinued from the study secondary to an AE unless the AE can be determined to be unrelated to treatment. If a participant is replaced after dosing, then the replacement participant will be assigned the original participant's number plus [REDACTED]. The replacement participant will receive the same treatment as the participant being replaced but a new participant number will be assigned to him or her. For example, Participant [REDACTED] would be replaced by Participant [REDACTED].

Study treatment will be dispensed at the study visits as listed in Schedule of Activities ([Section 2](#)).

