Part 2C will enroll a minimum of 20 participants per dose level of BMS-986207. One or two doses are planned to be evaluated and selected from the range of doses assessed as tolerable and not exceeding the maximum tolerated dose in Part 1C. If two doses will be tested at the Sponsor's discretion, participants will be randomized in a 1:2 ratio schema between the highest dose selected in Part 1C and the next lower dose, after at least 10 participants will have been tested at the dose found safe in Part 1C.

Continuous evaluation of toxicity events will also be performed in this part of the study. If, at any time, the aggregate rate of treatment-related toxicities meeting DLT criteria exceeds 33% in Parts 2A or 2B, the findings will be discussed and further enrollment may be interrupted. In addition, a more guided continuous safety monitoring will be implemented in Part 2C, 1L NSCLC expansion, using a Bayesian framework and specific criteria based on a posterior probability of a DLT rate exceeding 33% implemented starting with n=6 ([Table 10.3.8-1](#)). Depending on the nature and

grade of the toxicity, and after assessing the risk/benefit ratio, a new BMS-986207 dose for all participants, including those currently on treatment, may be initiated at a lower dose level.

Participants with an outcome of unconfirmed progressive disease, stable disease (SD), partial response (PR), or complete response (CR), at the end of a given cycle, will continue to the next treatment cycle. Participants will be allowed to continue study treatment until the first occurrence of any of the following:

- Completion of the maximum number of cycles
- Confirmed PD (see [Section 5.1.4](#))
- Clinical deterioration suggesting that no further benefit from treatment is likely
- Intolerability to therapy
- Participant meets criteria for discontinuation of study treatment as shown in [Section 8.1](#)

5.1.2.8 *Treatment with Additional Cycles Beyond 24 Weeks (Parts 1A, 1B, 2A, and 2B)*

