7.4.1 Dose Limiting Toxicities

For the purpose of guiding dose escalation, DLTs will be defined based on the incidence, intensity, and duration of AEs for which no clear alternative cause is identified. The DLT period will be 28 days (4 weeks) in Parts 1A and 1B. The DLT period for Part 1C will be 42 days (6 weeks).

For the purpose of participant management, any AE that meets DLT criteria, regardless of the cycle in which it occurs, will lead to discontinuation of study drug unless the Investigator determines that only 1 of the agents must be discontinued due to toxicity attributed to that agent alone. Participants who withdraw from the study during the 4-week DLT evaluation period (6-week DLT evaluation period for Parts 1C and 2C) for reasons other than a DLT may be replaced with a new participant at the same dose level. The incidence of DLTs during the 4-week DLT evaluation period (6-week DLT evaluation period for Parts 1C and 2C) will be used in dose escalation decisions and to define the MTD. AEs occurring after the 4-week DLT period (6-week DLT evaluation period for Parts 1C and 2C) will be considered for the purposes of defining the RP2D upon agreement between the Sponsor, Medical Monitor, and Investigators.

Participants experiencing a DLT will not be retreated with study drug, and will enter the safety follow-up period of the study. DLTs occurring after the 4-week (or 6-week period for Parts 1C and 2C) DLT observation period will be accounted for in determining the RP2D for expansion.

AEs will be graded according to the NCI CTCAE v4.03.

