10.3.8 Interim Analyses for Parts 2A, 2B, and 2C

The expansion phase of this study (Part 2A and Part 2B) employs a 2-stage design framework. Therefore, there will be an interim analysis as planned when an adequate number of participants have response-evaluable data. Additional interim analyses may also be performed for administrative purposes or publications. No formal inferences requiring any adjustment to statistical significance level will be performed.

For Part 2C, interim analyses may also be performed for administrative purposes or publications prior to the final database lock. No formal inferences requiring any adjustment to statistical significance level will be performed. Continuous safety monitoring will be implemented in Part

2C to further evaluate the safety of the triplet combination in the NSCLC population, in addition to that in Part 1C, as described below.

A Bayesian framework will be utilized for continuous monitoring of toxicity in Part 2C based on AEs meeting DLT criteria.⁴⁶ Observed incidence rates of treatment-related toxicities meeting DLT criteria (defined in [Section 7.4.1](#)) will be evaluated relative to a boundary (number of DLTs) associated with higher chance of the true DLT rate exceeding 33%.

Bayesian safety monitoring boundaries are established using a non-informative prior, Beta (0.5, 0.5). The posterior distribution is Beta ($0.5+n$, $0.5+(m-n)$), where m is number of treated Part 2C participants and n is the subset of these m participants who experience treatment-related toxicities meeting DLT criteria. All treated Part 2C participants are considered evaluable. The criterion for excess toxicity is based on a posterior probability (PP) of treated Part 2C participants with toxicities meeting DLT criteria $> 33\% \mid$ cumulative data exceeding 80%. If the criterion is met during continuous monitoring in Part 2C, there is greater than 80% PP that the DLT rate exceeds 33%; based on the observed data, the dose level may be re-evaluated and, based on the totality of data, a lower dose may be administered to the remaining participants. The cutoff number of participants with DLT needed to meet the criterion depends on the number of evaluable participants, with a final boundary of 14 participants with a DLT out of 37 or more.

Table 10.3.8-1: Safety Monitoring Boundaries for AEs Meeting DLT Criteria in Part 2C

Number of evaluable participants	Minimum Number of participants with AE meting DLT criteria
4 -6	3
7-8	4
9-11	5

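### In the open-label randomised cohorts (CRC, and Part 2C if two doses are tested), a replacement inherits the arm of the person replaced, so that slot is not randomised and its arm can be known beforehand

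*Combined protocol and SAP*

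**What the plan says.** Section 7.2 (Method of Treatment Assignment) covers the whole study. For the expansion phase it says that "participants with CRC will be randomized in a 1:1 manner to either BMS-986207 monotherapy, or combination therapy with BMS-986207 and nivolumab", and gives the purpose as "to eliminate the possibility of enrollment bias". Later in the same section come the replacement rules. One limits who is replaced, allowing it after an adverse event only where study treatment is judged not to be the cause; it begins "Participants will not be replaced if they are discontinued from the study secondary to an AE unless the AE can be determined". The other fixes what the newcomer receives: "The replacement participant will receive the same treatment as the participant being replaced". A participant who replaces someone already dosed gets a number built from that person's number, and participant numbers are site-specific.

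For Part 2C, Section 5.1.2.7 says that with two doses "participants will be randomized in a 1:2 ratio schema between the highest dose selected in Part 1C and the next lower dose", starting "after at least 10 participants will have been tested at the dose found safe in Part 1C". Section 7.4.1 says that people who withdraw during the DLT period, expressly including a 6-week period for Part 2C, "for reasons other than a DLT may be replaced with a new participant at the same dose level". For toxicity monitoring, Section 10.3.8 says: "All treated Part 2C participants are considered evaluable".

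Section 7.3 describes the study as open-label and also as non-randomised.

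**The concern.** Inheriting the treatment of the person replaced is natural in dose-escalation cohorts, where the aim is to fill a dose level with DLT-evaluable people. It does not fit a randomised cohort. When treatment is open and the vacant slot has a fixed arm, whoever fills it can be chosen with that arm in mind. That is the enrolment bias which Section 7.2 says the CRC randomisation is there to prevent.

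What is at stake is whether the two CRC arms, and the two Part 2C doses, hold comparable participants. The synopsis gives optimal dose selection for the recommended Phase 2 dose as one aim of Part 2C, and that involves setting the dose groups beside each other.

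**Working it through.** This is a question about a procedure, so the check sets the provisions side by side.

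1. **Are the cohorts randomised?** CRC: yes, 1:1 (Section 7.2). Part 2C: only if two doses are tested, and only after the lead-in of at least 10 participants at one dose (Section 5.1.2.7). If the total is 40 (Section 10.1.3.2) and the lead-in is exactly 10, then 40 − 10 = 30 are randomised. At 1:2 the higher dose ends with 10 + 30/3 = 20 and the lower with 30 × 2/3 = 20, matching the planned minimum of 20 per dose. So the point can concern at most the randomised portion of Part 2C.

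2. **Does the replacement rule reach them?** Section 7.2 places its rule in the general assignment section, without limiting it to Part 1 or exempting randomised cohorts. Section 7.4.1 names Part 2C. For CRC the reach is less direct: Section 7.4.1 defines no DLT period for Parts 2A or 2B, so only the general wording of Section 7.2 applies.

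3. **Is the slot's arm open to the site beforehand?** The study is open-label, so the site knows what the departing participant received. The rule fixes the newcomer's treatment to match, and the numbering ties the newcomer to the original. No passage provides for re-randomising, concealing the slot or leaving replacements out of the analysis. Foreknowledge is an inference, but it follows from the rules as written.

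4. **Does anything require same-arm replacement in Part 2C?** Not the toxicity boundary: Section 10.3.8 counts every treated Part 2C participant, including one who leaves early.

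5. **Can the effect be sized?** That needs a replacement rate and the difference in prognosis between selected and unselected candidates. The protocol gives neither.

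Steps 1 to 3 establish the defect, step 4 shows that removing it costs the toxicity rule nothing, and step 5 limits what can be claimed.

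**The case against.** **Scope.** Replacement is optional, and discontinuations for treatment-related adverse events are excluded. Part 2C is affected only if the sponsor chooses two doses. CRC replacement is barely provided for, and because Section 5.5.2.1 already reports pharmacokinetic data from Part 2A, an edit cannot reach those participants. All of this stands and narrows the point.

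**No formal comparison.** Section 3.1 says no hypotheses are formally evaluated. Section 10.1.3 judges each CRC cohort against historic and target rates, and each Part 2C dose against 36% and 56%. Randomisation does not protect those single-arm readings, and the lead-in is itself enrolled at a known dose. This also stands; what remains is comparability between arms and doses.

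**Two stronger readings that the documents do not support.**

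A reader might infer a replacement rate of up to a third from Part 1C, where 4 of 6 participants at 1200 mg were DLT-evaluable. Non-evaluability is not dropout, and Part 1C enrolled pretreated patients whereas Part 2C is first-line. Nor can a rate be applied to 39 CRC participants: that is 24 + 15, two unequal targets, whereas 1:1 allocation yields about 30 by the time the smaller arm is full.

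A reader might also infer that the Part 2C false-signal chance rises. The plan's own figure reproduces: with 20 participants, a cutoff of 11 and a true ORR of 36%, P(X ≥ 11) = 6.5%. Suppose r replacements have an ORR d higher, and sum Bin(20 − r, 0.36) with Bin(r, 0.36 + d), taking r = 3 or 5 and d = 0.10 or 0.20 (all assumed).

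- If those replaced leave the denominator (n = 20, cutoff 11), the chance is 8.4% to 14.4%.
- If they stay in as non-responders (n = 23 or 25), the Section 10.1.3.2 posterior criteria give cutoffs of 13 and 14, and the chance is 0.4% to 1.6%, below 6.5%.

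Section 10.3.1 bases the final analysis on the treated population, and someone who leaves within 6 weeks can hardly have a confirmed response (first scan near week 6, confirmation at least 4 weeks later). An increase therefore needs a denominator that the final analysis does not use, such as response-evaluable participants only. Even the direction of the effect on this decision rule depends on assumptions.

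**Conclusion.** The point holds as a defect in the allocation rule. Followed as written, the protocol leaves each replaced participant's slot unrandomised in cohorts that it otherwise randomises, and lets the arm be known before the candidate is chosen. The consequence is reduced comparability of the CRC arms and of the two Part 2C doses.

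Its size is unknown. It is limited to replaced participants, to Part 2C once two-dose randomisation has started, and to any CRC enrolment still to come. It rests on one inference: that the site connects the vacant slot with the treatment of the person who left. It would be wrong to conclude that the randomisation as a whole is invalid, or that a decision error has been shown to be inflated. This is a cheap improvement worth making, not a threat to the study's main conclusions.

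**What to change.** - Limit the same-treatment rule in Section 7.2 and the same-dose rule in Section 7.4.1 to the non-randomised cohorts: Parts 1A, 1B and 1C; HCC and ovarian cancer in Part 2B; and Part 2C before randomisation starts or if only one dose is tested.
- For randomised CRC and two-dose Part 2C, state that any participant added after a discontinuation takes the next unused assignment on the central IRT list, concealed from the site until eligibility is confirmed, and that the original participant stays in the treated population.
- In the same edit, reconcile Section 7.3's description of the study as non-randomised with Sections 7.2 and 5.1.2.7, and mention the Part 2C randomisation in Section 7.2, which omits it.

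The cost is about one sentence in each of Sections 7.2 and 7.4.1, a wording correction in Section 7.3 and an IRT setting. The downside is that final arm sizes may differ from target by a few participants.
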